4. STUDY VARIABLES

4.1. Demographic and Baseline Characteristics

Baseline characteristics will include standard demography (eg, age, race, weight, height, etc), disease characteristics including detailed cardiovascular and pancreatitis history, medication history, daily symptom Questionnaire, Symptom and Dietary Impact Questionnaire, and screening laboratory measurements for each patient.

4.2. Primary and Secondary Endpoints

4.2.1. Primary Endpoint

The primary endpoint is the percent lowering of TG levels from baseline following 12 weeks of repeated IV doses of evinacumab in the subset of patients with a documented history of sHTG (TG ≥ 1000 mg/dL [11.3 mmol/L]), a TG level of at least 500 mg/dL (5.6 mmol/L) at screening, a history of acute pancreatitis, and without LOF mutations in genes in the LPL pathway. (For patients randomized to evinacumab, baseline is defined as the period prior to the double-blind period; for patients randomized to placebo, baseline is defined as the period prior to the single-blind period.)

4.2.2. Secondary Endpoints

The secondary endpoints of the study are:

- Percent TG lowering from baseline following 2 to 24 weeks of repeated IV doses of evinacumab overall and subgroups with homozygous or compound heterozygous LOF mutations, heterozygous LOF mutations, and without LOF mutations in genes in the LPL pathway
- Changes in patient reported abdominal and GI symptoms, dietary habits, and symptom/dietary impact measures

- Degree of pancreatic injury/inflammation through ¹⁸F-FDG-PET imaging at baseline (placebo run-in) and change from baseline following 12 weeks of treatment with evinacumab as assessed by ¹⁸F-FDG standardized uptake values SUV_{max} and SUV_{mean}
- Degree of pancreatic injury/inflammation through DW-MRI at baseline (placebo run-in period) and the change from baseline following 12 and 24 weeks of treatment with evinacumab as assessed by ADC
- The total evinacumab concentrations, total ANGPTL3 concentrations, and ADA during the evinacumab treatment and follow-up periods
- Incidence and severity of treatment-emergent adverse event (TEAEs), SAEs, laboratory abnormalities, and other safety variables in patients treated with evinacumab

4.2.3. Exploratory Endpoints

The exploratory endpoints of the study are:

- Change from baseline in pancreatic injury/inflammation in the placebo run-in period and following treatment with evinacumab as assessed by biochemical markers (amylase, lipase, hsCRP, IL-6 and other inflammatory markers)
- Incidence of recurrent acute pancreatitis overall and in subgroups with homozygous or compound heterozygous LOF mutations, heterozygous LOF mutations, and without LOF mutations in genes in the LPL pathway
- Incidence of medical visits/hospitalizations for abdominal pain or pancreatitis, medical visits/hospitalizations for pancreatitis, and medical visits/hospitalizations for cardiovascular disease
- Degree of pancreatic injury/inflammation through T2-MRI at baseline (placebo run-in period) and the change from baseline following 12 and 24 weeks of treatment with evinacumab as assessed by T2 intensity and T2 relaxation time
- Degree of pancreatic injury/inflammation through ¹⁸F-FDG-PET imaging at baseline (placebo run-in) and change from baseline following 12 weeks of treatment with evinacumab as assessed by ¹⁸F-FDG Ki or Kpatlak
- Percent change from baseline in lipid parameters (eg, TC, TG, non-HDL-C, LDL-C, HDL-C, APOB, FFA, APOA-I) and lipoprotein subfraction composition (eg, CM, VLDL, IDL, LDL, HDL, particle cholesterol, TG content, and apolipoprotein composition) after ultracentrifugation at 16 weeks and 28 weeks
- Change from baseline in metabolic parameters (fasting blood glucose, insulin, C-peptide, HbA1c) after 12 and 24 weeks of evinacumab treatment
- Percent change from baseline in post heparin LPL activity after evinacumab treatment overall and by LPL gene mutations
- Change from baseline in ¹⁸F-FDG-PET in atherosclerotic plaque (TBR) in carotids and/or aorta
- Change from baseline in liver fat fraction as measured by MRI

4.3. Pharmacokinetic Variables

Pharmacokinetic variables may include, but are not limited to, the following:

- Total evinacumab concentrations in serum over time
- C_{\max}
- C_{trough}

4.4. Anti-Drug Antibody Variables

Anti-drug antibody variables include status (positive or negative) and titer as follows:

- Treatment emergent - defined as any post-dose positive ADA assay response when the pre-dose baseline ADA results are negative
- Treatment-boosted - defined as any post-dose positive ADA assay response that has titer at least 9-fold over the pre-dose baseline titer when pre-dose baseline ADA results are positive

The definition of persistent and transient ADA will be defined a priori in the statistical analysis plan (SAP).

- Titer values
- Titer category
 - Low (titer <1,000)
 - Moderate (1,000 \leq titer \leq 10,000)
 - High (titer >10,000)

Samples positive in the ADA assay will be assessed for neutralizing activity.

5. STUDY DESIGN

5.1. Study Description and Duration

This is a phase 2, randomized, placebo-controlled, study designed to evaluate the efficacy and safety of repeated doses of evinacumab in adult patients with severe HTG. Up to approximately 50 patients will be enrolled, randomized 2:1 (evinacumab:placebo) to receive evinacumab or placebo.

[figure not shown]
The study consists of a screening period of up to 37 days (which includes day -66 to day -59 [visit 1], day -58 to -52 [visit 1b], and day -51 to -39 [visit 2]), a baseline/single-blind placebo run in period (day -28 to day -1), a 12-week double-blind treatment period (day 1 to day 85), a single-blind 12-week treatment period (day 86 to day 169), and an off-treatment follow-up period (week 24 [day 170] to week 44 [day 309]).

The following cohorts will be enrolled based upon information (or lack of information) on genotype in the patient's medical history at screening:

1. Cohort 1: FCS due to complete LPL deficiency. Approximately 6 to 9 patients will be enrolled. This cohort consists of patients:
 - with known homozygous or compound heterozygous null LPL, GPIHBP1, or APOC2 LOF mutations
2. Cohort 2: Multifactorial chylomicronemia with partial LPL deficiency. Approximately 9 to 12 patients will be enrolled. This cohort consists of patients:
 - with known heterozygous null LPL, GPIHBP1, or APOC2 LOF mutations, or
 - with uncharacterized or known non-null LOF LPL pathway gene mutations (LPL, apoC2, apoA5, LMF1 and GPIHBP1)
3. Cohort 3: Multifactorial chylomicronemia. Approximately 15 to 27 patients will be enrolled. This cohort consists of patients not included in cohorts 1 or 2 above:
 - with other monogenic or polygenic causes of sHTG (eg, CGKR, CREB3L3, E2/E2 dysbetalipoproteinemia), or
 - without genotype information

A study flow diagram is in [Figure 1](#).

Figure 1: Study Flow Diagram

Screening (Day -66 to Day -29)

During the screening period, all patients will undergo the informed consent process and standard screening procedures. Laboratory assessments used to determine eligibility may be repeated once during the screening period. Patients who do not meet eligibility criteria during the initial screening may rescreen only once; only the assessments that did not meet eligibility criteria initially are required to be repeated, if rescreening occurs within the screening period. Patients who are rescreened after the screening window ends must re-consent for study participation and repeat all screening procedures.

After confirmation of eligibility at visit 2, all patients will receive an IV bolus of 60 IU of heparin per kg of body weight and a blood sample will be collected to assess baseline level of LPL enzyme activity.

Assignment into 1 of the 3 cohorts and enrollment into the study will occur at visit 3 for patients meeting eligibility.

If enrollment into a specific cohort has reached the maximum number allowed, the patient will not be eligible for enrollment.

Baseline/Single-Blind Placebo Run-in Period (Day -28 to Day -1)

Principal investigators, study site personnel, and the Regeneron study team will be unblinded to treatment, but study patients will not. On day -28, all patients will receive a single IV placebo infusion. Patients will be closely monitored for a minimum of 120 minutes after IV administration of placebo on day -28.

Double-Blind Treatment Period (Day 1 to Day 85)

Principal investigators, study site personnel, study patients and the Regeneron study team will all be blinded to treatment during the double-blind treatment period.

Patients will be randomized 2:1 (evinacumab:placebo) to receive either evinacumab administered IV at a dose of 15 mg/kg or matching placebo every 4 weeks (± 4 days) on days 1, 29, and 57. Patients will be closely monitored for a minimum of 120 minutes after IV administration of evinacumab or matching placebo on days 1, 29, and 57.

Stable doses of other triglyceride-lowering therapies, such as fibrates, statins, omega-3s, and niacin are allowed during the study. Patients may not take Glybera[®], mipomersen, or lomitapide during the study.

Efficacy and safety procedures and completion of the pancreatitis daily symptom questionnaire and symptom/dietary impact questionnaire will be performed as outlined in the schedule of events. Imaging correlates of pancreatic health will be assessed by ¹⁸F-FDG PET, by DW-MRI, and by T2-MRI.

Serum samples for the determination of total evinacumab, total ANGPTL3, and anti-drug (anti-evinacumab) antibodies (ADA) will be collected.

Serum and plasma samples will be collected for analysis of additional biomarkers, including amylase and lipase.

Single-Blind Treatment Period (Day 86 to Day 169)

All patients who complete the double-blind treatment period will receive evinacumab administered IV at a dose of 15 mg/kg every 4 weeks (± 4 days) on days 85, 113, and 141.

Stable doses of other triglyceride-lowering therapies, such as fibrates, statins, omega-3s, and niacin are allowed during the study. Glybera[®], mipomersen, or lomitapide are prohibited during the study.

Efficacy and safety procedures and completion of the pancreatitis daily symptom questionnaire and symptom/dietary impact questionnaire will be performed as outlined in the schedule of events. Patients should fast for a minimum of 8 hours prior to any blood draws. Imaging correlates of pancreatic health will be assessed by DW-MRI.

Serum samples for the determination of total evinacumab, total ANGPTL3, and anti-drug (anti-evinacumab) antibodies (ADA) will be collected.

Serum and plasma samples will be collected for analysis of additional biomarkers, including amylase and lipase.

Off-Drug Treatment Follow-up Period (Day 170 to Day 309 [End-of-Study])

Efficacy and safety procedures will be performed as outlined in the Schedule of Events.

Throughout the Study

Patients will be reminded at visits and during phone calls to adhere to a highly effective birth control method. Pregnancy status of female patients of childbearing potential and of female partners (of child-bearing potential) of male patients will be monitored throughout the study and for 24 weeks post the last dose of study drug.

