14. History of malignancy within 5 years prior to screening (other than successfully treated nonmetastatic cutaneous squamous cell or basal cell carcinoma and or localized carcinoma in situ of the cervix)
15. Any medical or psychiatric condition that, in the opinion of the investigator, would place patient at risk, interfere with participation in the study or interfere with the interpretation of the study results (eg, cirrhosis or chronic active hepatitis, nephrotic syndrome, uncontrolled diabetes, uncontrolled hypertension)
16. Previous treatment with Glybera® in the past 5 years or treatment with lomitapide or mipomersen in the past 6 months
17. Positive serum hCG pregnancy test at the screening visit
18. Creatine phosphokinase (CPK) $\geq 3x$ upper limit of normal (ULN) at the screening visit
19. Aspartate aminotransferase (AST) or alanine aminotransferase (ALT) $\geq 3x$ ULN
20. Thyroid-stimulating hormone (TSH) >1.5 ULN or $<$ lower limit of normal
21. Platelet count $<75,000$
22. Any patient who is the investigator or any sub-investigator, research assistant, study coordinator, or other staff directly involved in the conduct of the protocol, or a family member of staff involved in the conduct of the protocol
23. Pregnant or breast feeding women
24. Women of childbearing potential (WOCBP)* who are unwilling to practice a highly effective birth control method prior to the initial dose, during the study, and for 24 weeks after the last dose of study drug. Highly effective contraceptive measures include:
 - Stable use of combined (estrogen and progestogen containing) hormonal contraception associated with inhibition of ovulation initiated 2 or more menstrual cycles prior to screening:

- oral
- intravaginal
- transdermal
- Stable use of progestogen-only hormonal contraception associated with inhibition of ovulation initiated 2 or more menstrual cycles prior to screening:
 - oral
 - injectable
 - implantable
- intrauterine device (IUD)
- intrauterine hormone-releasing system (IUS)
- bilateral tubal ligation
- Vasectomized partner. Note: Vasectomized partner is a highly effective birth control method provided that the partner is the sole sexual partner of the woman of child bearing potential trial participant and that the vasectomized partner has received medical assessment of the surgical success

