7.4.2. Study Drug Discontinuation

Patients who permanently discontinue from study drug before entering the double-blind treatment period (day 1, week 0) will be contacted to assess any adverse events (AEs) but will not be asked to return for the remaining study visits.

Patients who permanently discontinue from study drug during the double-blind treatment period will be asked to return to the clinic within 5 days for an early termination visit consisting of week 12 study assessments; these patients will then enter the off-drug treatment follow-up period.

Patients who are permanently withdrawn from study drug during the single-blind treatment period will be asked to return to the clinic for an early termination visit consisting of week 24 study

assessments. After the early termination visit, patients will enter the off-drug treatment follow-up period.

Patients who are unable or unwilling to attend the study visits as described above should still be followed for at least 24 weeks from the last dose of study drug or up to recovery or stabilization of any AE to be followed-up as specified in this protocol, whichever comes last. The assessments completed should include pregnancy testing for WOCBP. A final end of study visit should take place with assessments as specified in the end of study visit (ie, follow up visit) at 24 weeks after the premature discontinuation of study drug.

Sexually active males and WOCBP who discontinue the study prematurely should be reminded at the early termination visit following treatment discontinuation to maintain the contraceptive measures (as described in Section 6.2.2) for 24 weeks after the last dose of study drug. At this visit, WOCBP will be provided a sufficient number of urine pregnancy tests with instructions to test for pregnancy 4 weeks after this visit and every 4 weeks (Q4W) thereafter. The patient will also be notified of Q4W follow-up phone calls to confirm continued contraception use, to obtain results of urine pregnancy tests, and to obtain information on whether pregnancy has occurred in WOCBP and in female partners of male patients.

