12. Lipids and lipoproteins, total cholesterol, LDL-C, HDL-C, TG, APOB, APOA1, and Lp(a) will be measured except at visit 1 and 1b.
13. At visit 1 and visit 1b, only total cholesterol, LDL-C, HDL-C, and TG will be measured.
14. Lipoprotein lipase level enzyme activity will be measured in fasting plasma collected at visit 2 only after eligibility has been confirmed by screening procedures at visit 1 and visit 1b.

15. Questionnaires should be completed daily for 7 days prior to each visit except for visit 3 (to be completed daily for the duration between visit 2 and visit 3).
16. Patients should be reminded by phone call 1 week prior to their visit to complete questionnaires.
17. Electrocardiogram should be performed before blood is drawn during visits that require blood draws.
18. In addition to assessment of adverse events at each visit, investigators should also ask patients if they have had any changes in abdominal symptoms and/or medical clinic visits for abdominal symptoms.
19. Confirm required contraception use and pregnancy status of female patients of childbearing potential and female partners (of child-bearing potential) of male patients will be monitored at clinic visits and by phone call for 24 weeks post the last dose of study drug. Women of childbearing potential will be provided urine pregnancy tests with instructions to test for pregnancy on days corresponding to phone call visits or Q4W if patients do not attend regularly scheduled visits.
20. Imaging may be performed up to 1 week prior to the visit and may be on the same day of the visit (for visit 3, MRI can be done on the same day or up to 4 days after visit 3). If done on the day of the visit, vital signs, ECG and blood draws after an 8-hour fast should be completed prior to the imaging procedures. Imaging procedures should be performed prior to study drug infusion.
21. PK samples will also be used for the analysis of total ANGPTL3.
22. In addition to the PK sample collected prior to drug administration, a PK sample should be obtained immediately after the end of each infusion.

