If a WOCBP is lost to follow-up, sites should attempt a minimum of 2 telephone calls. If the patient cannot be reached on the second attempt, a formal letter will be issued from the site to the patient that reminds the patient of the importance of continued use of highly effective contraception use for at least 6 months after the last dose of study drug.

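### Completers get exactly 24 weeks of post-dose pregnancy and AE follow-up on nominal days, but the Table 1 visit windows do not guarantee it, and Protocol Section 8.1.2 gives two contraception intervals

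*Protocol*

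**What the plan says.** **Monitoring.** Protocol Section 5.1 (Throughout the Study) says that the pregnancy status of women of childbearing potential, and of male patients' partners, "will be monitored throughout the study and for 24 weeks post the last dose of study drug". Footnote 19 to Table 1 (Section 8.1.1) names the means: status "will be monitored at clinic visits and by phone call for 24 weeks post the last dose of study drug".

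**Schedule.** Section 5.1 places the single-blind infusions "on days 85, 113, and 141". Table 1 gives the visit 12 infusion a window of ± 4 days. It puts visit 18, the end-of-study visit with the final serum pregnancy test and adverse event (AE) contact, at day 309 ± 5. Nothing is scheduled after visit 18.

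**Contraception.** Exclusion criterion 24 (Section 6.2.2) requires it "prior to the initial dose, during the study, and for 24 weeks after the last dose of study drug", and criterion 25 uses the same 24 weeks for men. Section 7.4.2 tells early discontinuers to continue "for 24 weeks after the last dose of study drug", and Section 8.1.2 repeats this. The last paragraph of Section 8.1.2 differs. The letter to a woman lost to follow-up is to stress the "importance of continued use of highly effective contraception use for at least 6 months after the last dose of study drug".

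**Early discontinuers.** Sections 7.4.2 and 8.1.2 set a minimum of 24 weeks of follow-up from the last dose, with four-weekly calls and home pregnancy tests.

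**Adverse events.** Protocol Section 9.4.6 collects AE information up to the patient's last study visit. SAP Section 4.8.1 runs the single-blind treatment-emergent period to the last dose plus 168 days.

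**The concern.** The 24-week statement counts from the last dose. The visit that carries the final scheduled test and contact is fixed by study day, and so is the last dose. When two such dates each have a window and the nominal gap equals the stated interval exactly, there is no slack: any patient whose last dose slips later by more than visit 18 does is seen before 24 weeks are up.

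Section 3.2.1 lists embryofetal toxicity among the important potential risks and relies on a mitigation plan for it. If visit 18 comes early, the final scheduled pregnancy test precedes the end of the stated interval. A pregnancy in the remaining days would then come to light only if the patient reported it or the site made an unscheduled contact. For safety reporting, non-serious AEs in those days would go uncollected although the SAP would count them as treatment-emergent. The two contraception intervals matter because different patients would be told different things within one protocol section.

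**Working it through.** **Inputs.** Last dose: day 141 ± 4, so day 137 to 145 (Table 1, visit 12). Final visit: day 309 ± 5, so day 304 to 314 (Table 1, visit 18). Stated interval: 24 weeks × 7 = 168 days (Section 5.1, footnote 19). The windows are read as the table shows them, around nominal study days.

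**Step 1. Reproduce the plan's own figure.** 309 − 141 = 168 days; 168 / 7 = 24.0 weeks. The nominal schedule matches the statement exactly.

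**Step 2. Range on schedule.**

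| Case | Calculation | Days | Weeks | Against 168 |
|---|---|---|---|---|
| Shortest | (309 − 5) − (141 + 4) = 304 − 145 | 159 | 22.7 | 9 short |
| Nominal | 309 − 141 | 168 | 24.0 | equal |
| Longest | (309 + 5) − (141 − 4) = 314 − 137 | 177 | 25.3 | 9 over |

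**Step 3. Is the shortfall a single corner case?** Let the dose be shifted by *b* days (−4 to 4) and the visit by *a* days (−5 to 5), giving 9 × 11 = 99 combinations. The gap is below 168 when *a* < *b*. For each *b* there are *b* + 5 such values of *a*, so the count is 1 + 2 + … + 9 = 45. The other 54 give 168 days or more. The shortfalls sum to 165 days, a mean of 165 / 45 = 3.7 days among the 45, and only one combination reaches 9 days. These are counts of permitted day pairs, not probabilities.

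**Step 4. Can 24 weeks be met inside the existing window?** The latest permitted dose is day 145. 145 + 168 = day 313, inside day 304 to 314. So 24 weeks is attainable for every permitted dose day.

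**Step 5. AE collection.** A patient dosed on day 145 and seen on day 304 stops contributing non-serious AEs at 159 days, against the SAP limit of 168: 168 − 159 = 9 days.

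**Step 6. The two contraception intervals.** Six calendar months is 181 to 184 days, so the letter is 181 − 168 = 13 to 184 − 168 = 16 days longer than 24 weeks. If a month meant four weeks, 6 × 28 = 168 and the two would agree. The protocol does call its four-weekly dosing monthly, but it does not define the term.

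**The case against.** The best defence is that the nominal schedule delivers exactly 24 weeks and that the duties run from the last dose, not from visit 18. Contraception (Section 6.2.2), pregnancy reporting within 24 weeks (Section 9.4.3) and monitoring (footnote 19) are all worded that way, so an early visit 18 cancels none of them. Section 9.4.2 also has serious AEs reported if the investigator learns of them and onset is within 30 days of the end of study; even at the shortest gap, 159 + 30 = 189 days. The tolerance is symmetric, at most 9 days, and falls in an off-drug period that is only summarised descriptively. The SAP's 168 days can be read as an outer limit for classifying events rather than a promise to observe to that day.

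Most of this stands. It rules out several stronger readings that a reader might infer:

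- *That the embryofetal risk mitigation is not delivered.* Section 3.2.1 describes the plan as including contraception requirements and does not define it by the date of last contact. Those requirements are unaffected by the visit window.
- *That three durations apply to one risk.* Apart from the letter, the protocol uses 24 weeks throughout. A visit window is a tolerance, not a stated duration. The letter concerns contraception, goes only to women already lost to follow-up, and read in calendar months is longer, so it does not weaken protection.
- *That about 45% of completers finish early.* The 45 of 99 becomes a probability only if all permitted days are equally likely and the two shifts are independent. The documents give no basis for that.
- *That follow-up falls short because it never reaches six months.* Nothing requires six months of monitoring.

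What the defence does not answer is that footnote 19 names clinic visits and phone calls as the means of monitoring, and Table 1 has none after visit 18. The duty may continue, but no scheduled contact or test supports it. Early discontinuers have an explicit 24-week minimum and completers do not.

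**Conclusion.** The point holds as a small, safety-relevant inconsistency. The 24-week interval is met on nominal days but not guaranteed for completers: on-schedule visits allow 159 to 177 days, a worst-case shortfall of 9 days in both the final scheduled pregnancy test and AE collection. Separately, Section 8.1.2 gives two contraception intervals, which differ by 13 to 16 days if months are calendar months.

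This assumes that the windows sit around nominal study days. If the ± 4 days instead applied to each dosing interval and accumulated over the five intervals from day 1 (141 + 20 = day 161) with visit 18 still possible on day 304, the shortest gap would be 304 − 161 = 143 days (20.4 weeks). The window printed for visit 12 argues against that reading.

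Sample size, power and the primary analysis are unaffected.

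**What to change.** Reconcile the visit 12 and visit 18 windows in Table 1 with the post-dose interval stated in Section 5.1 and footnote 19, counting from the actual last-dose date, so that the scheduled final test and AE contact are consistent with that interval. Check the result against the last dose plus 168 days in SAP Section 4.8.1.

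Reconcile the letter wording in Section 8.1.2 with the 24-week contraception text in Sections 6.2.2, 7.4.2 and 8.1.2. Which interval applies is for the sponsor's clinical team; this review does not choose one.

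The cost is protocol wording. If 24 weeks is kept, some visit 18 dates move later by up to 9 days (day 304 to day 313 for a day-145 dose), all within the existing window and with no added visit.
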